longitudinal mediation model will allow for the determination of how drug condition and baseline estradiol, AEA and 2-AG levels affects subjective anxiety across session time, which mediates changes in heart rate, blood pressure and salivary cortisol across session time. I hypothesize THC-induced increases in subjective anxiety mediate increases in heart rate, blood pressure and salivary cortisol across session time.

Significance.

The goal of this project is to determine the influence of estradiol and endocannabinoids on THC-induced increases in subjective anxiety and how this may mediate increases in heart rate, blood pressure and salivary cortisol. Cannabis and THC accessibility and consumption are increasing as medical and recreational use is being legalized across more states. Although there is evidence both low doses of cannabis and oral THC have some therapeutic effects, such as anxiolytic, analgesic and hunger stimulating effects, at moderate and higher doses the drugs can also produce serious unwanted effects including anxiety and paranoia (Zeiger et al., 2010; Crean et al., 2011). THC's effects vary across individuals, and may depend in part on body mass index, age, frequency of cannabis use and other variables such as hormone or endogenous cannabinoid levels (Wiley et al. 2014, D'Souza et al. 2008, Pope et al. 1996). Uninformed use of the substance could pose a public health risk, especially as recreational use is on the rise. A better understanding of individual differences in acute responses to THC will help to maximize the potential benefits and minimize adverse consequences of THC and cannabis-related products.

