Participants 60 healthy female volunteers who are occasional cannabis users (18-35 years, <11 uses of cannabis in past month) will be recruited by posters, advertisements, and word-of-mouth referrals, without regard to race or ethnicity. An undergraduate from the University of Chicago college will only be considered as a potential participant if she is within their 4th year of study. Potential participants will undergo a semi-structured clinical psychiatric interview (American Psychiatric Association, 2013) and provide information about current and lifetime history of drug use. Individuals taking any medications, or with serious psychiatric disorders such as psychosis or severe Post-Traumatic Stress Disorder or Obsessive Compulsive Disorder will be excluded. We will also exclude individuals with moderate or severe Substance Use Disorder, and those with BMI outside the normal range (less than 19 or more than 26), abnormal EKG, or pregnant or planning to be pregnant. Participants must have regular menstrual cycles and not be lactating or using hormonal contraceptives. Participant selection will be monitored throughout the study to ensure that the two groups, EFG and LFG, are matched on demographic characteristics, including age, race, education, SES, smoking, drinking, and drug use. Participants will be paid a \$180 for completing all sessions. They will also have the opportunity to win an additional \$8-\$35 based on experimental task performance.

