Statistical Analyses Sample Size Calculation: Sample size calculations were conducted using G*Power3.1 Software. Since there are no published data on effects of estradiol or eCB levels on response to THC a small effect size was assumed ($d = 0.3$). Recruiting 30 participants for each experimental group, 30 females in early follicular phase, 30 females in late follicular phase, for this study will allow for 80% power to detect an effect at alpha level $p = 0.05$.

A multilevel longitudinal mediation model will be used to analyze the collected data. Our independent variables include within-subjects drug dose and between subjects estradiol (EFG or LFG), AEA and 2-AG levels. Our mediator variable is subjective anxiety across session time. Our dependent outcome measures include heart rate, blood pressure and salivary cortisol across session time. A multilevel longitudinal mediation model will allow for the determination of how drug condition and baseline estradiol, AEA and 2-AG levels affects subjective anxiety across session time, which mediates changes in heart rate, blood pressure and salivary cortisol.

Expected Outcomes Based on several preclinical studies, I expect the LFG to have higher levels of estradiol and anandamide at baseline than the EFG, but no significant differences in baseline trait anxiety, anxiety sensitivity or salivary cortisol (Reed and Carr, 2000; Gorzalka and Dang, 2012; Monero-Lopez et al. 2018). Further, I expect that the effect of THC on subjective anxiety, heart rate and salivary cortisol will be greater in the LFG compared to the EFG, even after including any possible baseline differences in cortisol, trait anxiety or endocannabinoids as a covariate. Additionally, based on preliminary data and prior literature, I expect females with lower endocannabinoid levels, after controlling for cycle phase or estradiol levels, to experience larger increases in subjective anxiety, heart rate and report significantly greater subjective drug and mood effects of oral THC in a dose dependent manner (Hill et al. 2010). Finally, I expect THC-induced change in cortisol to mediate the increase in heart rate and greater subjective drug and mood effects. These results will contribute significantly to the small literature on individual differences in response to THC and lay a foundation for future

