sex-specific cannabis use guidelines, to prevent against THC-induced anxiety, paranoia, and psychosis, and new sex-specific cannabis use disorder treatment options.

Potential problems, Alternative strategies, and Limitations Several problems could arise. First, it may be difficult to recruit qualifying participants in the planned time frame. This seems unlikely since similar inclusion criteria have been used in prior studies within the lab and there has not been significant difficulty recruiting these individuals. But if this is the case, I will increase venues for advertising and identify new online recruitment sources. Second, the differences in responses to THC in females at different phases of their menstrual cycle may be too small to detect with this sample. This is possible, even though we based the sample size on a small effect size. If the findings look promising we would consider increasing our sample size or utilize the data as a pilot for a future study with a larger sample. Third, the two groups of females may differ in pre-capsule measures, such as mood states, cortisol levels, eCB levels, blood pressure or in demographic characteristics such as prior drug use. I will include any of these significant differences between groups as a covariate in the final analyses.

Literature Cited

American Psychiatric Association. (2013). Cautionary statement for forensic use of DSM-5. In *Diagnostic and statistical manual of mental disorders* (5th ed.). doi:10.1176/appi.books .9780890425596.744053

Craft, R. M., & Leitl, M. D. (2008). Gonadal hormone modulation of the behavioral effects of Δ9-tetrahydrocannabinol in male and female rats. *European Journal of Pharmacology*, 578(1), 37–42.

Crean, R. D., Crane, N. A., & Mason, B. J. (2011). An Evidence Based Review of Acute and Long-Term Effects of Cannabis Use on Executive Cognitive Functions. *Journal of Addiction Medicine*, 5(1), 1–8. <https://doi.org/10.1097/ADM.0b013e31820c23fa>

D'Souza, D. C., Ranganathan, M., Braley, G., Gueorguieva, R., Zimolo, Z., Cooper, T., ... Krystal, J. (2008). Blunted Psychotomimetic and Amnestic Effects of Δ-9-Tetrahydrocannabinol in Frequent Users of Cannabis. *Neuropsychopharmacology*, 33(10), 2505–2516. <https://doi.org/10.1038/sj.npp.1301643>

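### The phase groups are matched on factors that the Aim 1 model leaves out; prespecifying age and recent cannabis use, each with its product with drug, would be a cheap gain in precision

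*Combined protocol and SAP*

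**What the plan says.** The combined protocol and SAP deals with these factors in four places.

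- **Participants:** "Participant selection will be monitored throughout the study to ensure that the two groups, EFG and LFG, are matched on demographic characteristics". The list covers age, race, education and socioeconomic status, and smoking, drinking and drug use. No pairing, stratification or minimisation is described. The Approach section says that women are randomised to the early (EFG) or late (LFG) follicular group.
- **Statistical Analyses:** "Our independent variables include within-subjects drug dose and between subjects estradiol (EFG or LFG), AEA and 2-AG levels". Subjective anxiety is the mediator. No matching factor is listed, and Aim 3 gives the same set of terms.
- **Potential problems, Alternative strategies, and Limitations:** if the groups differ on pre-capsule measures or on demographic characteristics such as earlier drug use, "I will include any of these significant differences between groups as a covariate in the final analyses". Expected Outcomes also mentions covariates only in connection with possible baseline differences.
- **Significance:** the effects of THC "may depend in part on body mass index, age, frequency of cannabis use and other variables". Two of the factors named there, age and cannabis use, are also matching factors.

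**The concern.** The matching and the covariate rule work against each other. The better the groups are matched, the surer it is that the matched factors stay out of the model.

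Balancing a factor removes its contribution to chance differences between the groups. A model without that factor still counts its variance as error. The estimated standard error of the group contrast is then larger than its true sampling variability, so the test rejects less often than 5% under the null and gives up power.

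Only factors that change a woman's THC-minus-placebo response matter here. A factor that merely shifts her overall level cancels within woman. The Significance section suggests such modification for age and cannabis frequency, and for no other matching factor.

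At stake is precision for the Aim 1 comparison of EFG with LFG. The study has 60 women, and its own limitations section allows that the phase difference may be too small to detect.

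**Working it through.** **Inputs from the documents.** 30 women per group; "a small effect size was assumed ($d = 0.3"; "80% power to detect an effect at alpha level $p = 0.05". Sidedness, SD, within-woman correlation and test family are not given; two-sided tests are used here.

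**The plan's own figure.** A two-sample comparison at d = 0.3 with 30 per group has about 21% power, and 80% would need 175 per group. The repeated-measures interaction formula with f = 0.15 gives 78.6% with 4 measurements and correlation 0.5, or 80.0% with 2 measurements and correlation 0.667, but the documents state neither setting. The 80% is therefore not reproduced from what is written. That is a separate matter. To show the effect of adjustment on a readable scale, the power figures below use 0.736 SD of the THC-minus-placebo response, the effect at which a t-test with 30 per group (58 df) has 80% power.

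**Assumption.** R2 is the share of between-woman variance in the THC-minus-placebo response that the matched factors explain. The documents give no value, so a range is shown.

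**Formula for tight balance, factors omitted.**

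- Estimated SE / true SE = 1/√(1 − R2)
- Actual two-sided type I error = 2 × [1 − Φ(1.96/√(1 − R2))]

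At R2 = 0.10: ratio 1/√0.90 = 1.054; 1.96 × 1.054 = 2.066; type I error 3.9%.
At R2 = 0.25: ratio 1/√0.75 = 1.155; 1.96 × 1.155 = 2.263; type I error 2.4%.

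**Simulation.** 20,000 trials per row, two covariates, a woman-level t-test against the same comparison adjusted for both covariates. In the loose rows, random allocation is redrawn until neither covariate differs at p < 0.05.

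| Matching | R2 | Type I, unadjusted | Type I, adjusted | Power, unadjusted | Power, adjusted |
|---|---|---|---|---|---|
| Exact | 0 | 5.0% | 5.0% | 79.8% | 79.8% |
| Exact | 0.10 | 3.9% | 5.1% | 81.7% | 84.3% |
| Exact | 0.25 | 2.3% | 4.9% | 83.2% | 89.8% |
| Loose | 0 | 5.0% | 4.9% | 79.7% | 78.8% |
| Loose | 0.10 | 4.7% | 4.9% | 80.0% | 82.9% |
| Loose | 0.25 | 4.1% | 4.9% | 80.6% | 89.1% |
| None (simple randomisation) | 0.10 | 4.9% | 4.9% | 80.4% | 83.0% |
| None (simple randomisation) | 0.25 | 5.0% | 4.8% | 79.5% | 88.8% |

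Other exact-matching runs gave 3.7 to 3.9% at R2 0.10 and 2.4 to 2.7% at R2 0.25, so the last digit is simulation noise.

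**Does the covariate rule rescue the analysis?** In a simulation of sequential balancing on four factors, the significance rule brought in a factor in 0.0% of trials, so it was the same as the unadjusted analysis.

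**At the plan's own effect.** With d = 0.3 read as a difference in the THC-minus-placebo response and tight balance, adjustment moves power from 20.1% to 23.1% at R2 0.10 and from 18.6% to 25.4% at R2 0.20.

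**The case against.** A reader might infer that the Aim 1 error bars are certain to be too wide and that the test is certain to run below 5%. The documents do not support that, for four reasons.

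1. **Tightness of matching is unknown.** Selection is only monitored, allocation is random, and the limitations section anticipates that the groups may still differ on demographics. Under loose matching, most of the conservatism disappears. This stands.
2. **R2 is unknown and may be small.** The Significance section gives a possibility without a magnitude. Eligibility (ages 18 to 35, at most 10 uses in 30 days) narrows both predictors. For the other five factors, the documents give no support as modifiers of the THC response. This stands.
3. **The planned model is not a t-test on differences.** It is a multilevel longitudinal model with no stated random-effects structure. In a simulation with a random intercept only and four post-dose readings, the drug-by-phase test rejected 8 to 25% of the time under the null. That assumed subject-by-drug variance of 0.25 to 2 times the residual variance, exact matching and R2 of 0.10 to 0.25. The documents do not state that structure either, but they do not establish that the net error is conservative.
4. **Scope.** Aim 1 also relates responses to measured estradiol. Matching the groups does not balance factors along that continuous value, so the point covers only the EFG-versus-LFG contrast.

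These points limit the size and certainty of the standard-error distortion. They do not remove the power gain from adjustment, which appears in the table with or without matching.

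**Conclusion.** The inconsistency is in the text: factors important enough to match on are left out of the model, and the only rule that could admit them is switched off when matching works. Its cost is conditional on matching being achieved, on the factors modifying the THC response, and on an analysis that treats the woman as the unit for the phase-by-drug contrast.

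Under those conditions, type I error falls to about 3.8% (exact) or 4.7% (loose) at R2 0.10, and to about 2.4 to 2.6% or 4.1% at R2 0.25. Adjustment recovers about 2 to 3 and 7 to 9 power points respectively, at 0.736 SD. At R2 = 0 there is nothing to recover.

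The mechanism does not bias the contrast or produce false positives. It is best graded as an inexpensive precision improvement to consider. Confidence is good on what the text says, and low on the size.

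**What to change.** **Statistical Analyses.** State that the Aim 1 phase-by-drug model includes age and past-30-day cannabis use whatever the observed group differences. Each should enter as a main effect and as a product with drug, because a main effect alone cancels in the THC-minus-placebo contrast. Smoking and drinking are optional. Race, education and socioeconomic status need not enter, since they may each take several parameters. State the random-effects structure in the same place, because the error rate of this test depends on it.

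**Potential problems, Alternative strategies, and Limitations.** Add that the significance rule does not decide whether the prespecified factors enter.

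**Cost.** A few sentences and no new data, since both factors are needed for eligibility. About two between-woman degrees of freedom are used (58 to 56 in the simple comparison). If the factors do not predict the THC response, the loss is at most about 1 to 2 power points in the simulations.

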Aim 1: To examine whether high levels of estradiol augment the effect of THC on subjective anxiety, heart rate, blood pressure and salivary cortisol in females. To test this, female occasional cannabis users will receive a single dose of THC (0, 15 mg) during either the early follicular phase (days 1-8) when estradiol levels are low, or during the late follicular phase (days 9-14) when estradiol levels are high. Participants will attend two experimental sessions separated by at least four days, to allow for clearance of the drug. Plasma levels of estradiol, progesterone, and endocannabinoids, as well as salivary cortisol, physiological measures and subjective mood ratings will be obtained at the beginning of all three sessions. During the sessions, physiological measures, subjective ratings of drug effects and mood, and salivary cortisol will be obtained at regular intervals after drug consumption. I hypothesize THC will produce a greater increase in subjective anxiety, heart rate, blood pressure and salivary cortisol during the late follicular phase, and that this will be correlated with higher circulating levels of estradiol.

Aim 2: To examine whether low levels of circulating endocannabinoids augment the effects of THC on subjective anxiety, heart rate, blood pressure and salivary cortisol in females. To test this, the plasma samples mentioned above will also be analyzed for endocannabinoids, anandamide (AEA) and 2-arachidonoylglycerol (2-AG) levels. Baseline AEA and 2-AG levels will be compared to THC-induced increases in subjective anxiety, heart rate, blood pressure and salivary cortisol. I hypothesize females with lower endocannabinoid levels will exhibit greater THC-induced increases in subjective anxiety, heart rate, blood pressure and salivary cortisol levels.

Aim 3: To evaluate determine whether subjective anxiety mediates the physiological stress response after THC. To test this, I will use a multilevel longitudinal mediation model to analyze the collected data. Our independent variables will include within-subjects drug dose and between subjects estradiol (EFG or LFG), AEA and 2-AG levels. Our mediator variable will be subjective anxiety across session time. Our dependent outcome measures include heart rate, blood pressure and salivary cortisol across session time. A multilevel

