For this study we will use a mixed within- and between subject design to examine effects of THC (0 and 15 mg) in two groups of female occasional cannabis users: women tested in the early follicular phase of their menstrual cycle (EFG; N=30) and women tested in the late follicular phase (LFG; N=30). Occasional cannabis users will be defined as individuals who have used cannabis 10 or less occasions in the past thirty days. Females will be randomly assigned EFG or LFG groups. EFG women will be tested 1 to 8 days since the first day of menstruation and LFG women between days 9 and 14. Subjects will attend two four-hour experimental sessions in which they receive THC (15 mg THC) or placebo in counterbalanced order under double blind conditions. Plasma and saliva samples will be obtained before capsule consumption at the start of each session for baseline hormone, endocannabinoid and cortisol levels. The primary outcome measure is salivary cortisol, which will be measured both at baseline and periodically post-drug consumption. Secondary outcome measures include heart rate, blood pressure, body temperature, subjective drug effects (i.e. "feel drug effect"), and THC-induced anxiety. For Aim 1 we will examine THC-induced increases in cortisol in relation to baseline estradiol levels. For Aim 2 will examine THC-induced cortisol in relation to baseline endocannabinoid levels. For Aim 3 we will examine THC-induced increases in heart rate and subjective drug effects relative to THC-

induced increases in cortisol. The study will be approved by the Institutional Review Board at the University of Chicago, in accordance with the Code of Federal Regulations (Title 45, Part 46) adopted by the National Institutes of Health and the Office for Protection from Research Risks of the US Federal Government. The studies will be conducted in accordance with the Helsinki Declaration of 1964 (revised 1989) and the National Advisory Council on Drug Abuse Recommended Guidelines for the Administration of Drugs to Human Subjects.

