Orientation Session Participants will first participate in a 1-hour orientation session to provide informed consent, agree to the study conditions described above, complete the Trait Anxiety Inventory (Spielberger et al. 1971) and the Anxiety Sensitivity Inventory (Reiss et al. 1986), and practice questionnaires that will be administered throughout the sessions. Participants will be instructed to refrain from any use of drugs or alcohol for 24 before the experimental sessions. They will be advised that they must pass urine tests on the days of their experimental sessions for recent drug use including cannabis, and to pass these tests they should abstain from use for one week if they are light users (1-2 times per week) and for two weeks if they are heavier users (e.g., every other day). They will be told to have a normal night's sleep before the session and abstain from eating for at least 6 hours prior to their session. For blinding purposes, subjects will be told the capsules used in the study may contain a placebo, stimulant, cannabinoid-like drug, or sedative. The reason for blinding is we wish to study the pharmacological effects of this drug, without the possible confound of expectancies. We and others have shown that expectancies influence responses to drugs, in ways that might obscure true biological differences in the effects of the drug (see Mitchell et al. 1996; Kirk et al. 1998; Metrik et al. 2009; Heinz et al. 2013). Subjects will then practice the physiological measures and subjective questionnaires.

Experimental Session Timeline Participants will attend two experimental sessions lasting from 12:00 pm to 4:00 pm. Sessions are run from 12:00 pm to 4:00 pm to account for the diurnal rhythm of salivary cortisol—levels reach lowest levels at around midnight, start to rise at around 2:00 am to 3:00 am, reach a peak at around 8:30 am, and then slowly decrease back down to complete the cycle over 24 hours (Debono et al. 2009). Females in EFG will participate 1-8 days after first day of menstruation, at a time when both estradiol and progesterone levels are low (Barbieri et al. 2014). Females in the LFG will participate 9-14 days after first day of menstruation, at a time when estradiol levels are peaking or have just peaked, but progesterone levels remain low. The half-life of oral THC in infrequent users is about 1.3 days (Smith-Kielland et al. 1999). Therefore sessions will be scheduled with a minimum of 4 days to allow for washout.

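### Within one cycle, the 4-day gap puts a late-follicular woman's two sessions at opposite ends of days 9–14, tying session order to cycle day, and the EFG/LFG label in the model cannot show this

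*Combined protocol and SAP*

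**What the plan says.** - **Windows.** The Approach states: "EFG women will be tested 1 to 8 days since the first day of menstruation and LFG women between days 9 and 14". Each group has 30 women. Each woman has one THC and one placebo session, "in counterbalanced order under double blind conditions". It does not say that counterbalancing is done within each phase group.
- **Gap.** Experimental Session Timeline states: "Therefore sessions will be scheduled with a minimum of 4 days to allow for washout". Aim 1 likewise has "two experimental sessions separated by at least four days, to allow for clearance of the drug".
- **Estradiol in the LFG window.** Experimental Session Timeline words the window slightly differently: "Females in the LFG will participate 9-14 days after first day of menstruation". Of the hormone levels to be expected on those days, it says that testing is "at a time when estradiol levels are peaking or have just peaked, but progesterone levels remain low". Aim 1 simply calls estradiol high in that window. Neither place gives a peak day or estradiol values by day.
- **Measurement.** Blood for hormones is drawn before the capsule at each session. The Approach says that Aim 1 relates the cortisol response to baseline estradiol.
- **Model.** Statistical Analyses lists the independent variables as drug dose (within subjects) and, between subjects, estradiol with EFG and LFG as its levels, plus AEA and 2-AG. The same paragraph later mentions baseline estradiol, but the group label is the only coding it gives. It names no term for session order or cycle day. The covariate rule under Potential problems covers only variables on which the two groups differ significantly.
- **Cycle.** No section says whether a woman's two sessions must, or may not, fall in the same cycle.

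**The concern.** A 6-day window and a 4-day minimum gap leave little room. If an LFG woman completes both sessions in one cycle, one must be at the start of the window and the other at the end. Drug order then decides at which end she takes THC. Two things follow.

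First, the LFG label covers two distinct THC exposures, one early and one late in the window, and the listed model cannot tell them apart. The labels also treat days unevenly. EFG day 8 and LFG day 9 are adjacent but sit in opposite categories, while one LFG woman's two sessions, 4–5 days apart, sit in the same category.

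Second, each woman's THC-minus-placebo difference mixes drug with 4–5 days of cycle progression and with session order. That averages out within a phase group only if order is balanced within that group, which the protocol does not promise. At stake is how the Aim 1 phase contrast is read: which estradiol exposure it represents, and whether it is partly a difference in order split.

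**Working it through.** **Inputs.** LFG window days 9–14, EFG window days 1–8, 30 women per group and counterbalanced order (Approach); minimum gap 4 days (Aim 1 and Experimental Session Timeline).

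**1. Feasible same-cycle day pairs.** For session days a < b, require b − a ≥ 4.
- LFG, 9 ≤ a and b ≤ 14: a can be at most 10 and b at least 13. The pairs are (9,13), (9,14) and (10,14). Days 11–12 cannot be used.
- If the gap means four clear days (b − a ≥ 5), only (9,14) remains.
- If the wording in Experimental Session Timeline means cycle days 10–15, the pairs are (10,14), (10,15) and (11,15). They shift by one day and the structure is the same.
- EFG, days 1–8: ten pairs, with session 1 on days 1–4 and session 2 on days 5–8.

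**2. Share of LFG THC doses at the early end.** Let w be the share of LFG women tested within one cycle and p the share of those who receive THC first. The share forced to the early end is w × p. With p = 0.5 it is 0.5w: 0% at w = 0, and 50% (15 of 30) at w = 1. The documents do not give w.

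**3. Mean THC day, and its dependence on the order split.** Take w = 1 in both groups and weight feasible pairs equally (assumptions).
- LFG session 1: (9 + 9 + 10)/3 = 9.33. Session 2: (13 + 14 + 14)/3 = 13.67.
- EFG session 1: 20/10 = 2.0. Session 2: 70/10 = 7.0.
- Mean THC day = p × (session 1 mean) + (1 − p) × (session 2 mean).

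| THC-first : placebo-first | LFG mean THC day | EFG mean THC day | Difference |
|---|---|---|---|
| 15:15 in both groups | 11.50 | 4.50 | 7.00 |
| LFG 20:10, EFG 10:20 | 10.78 | 5.33 | 5.45 |
| LFG 10:20, EFG 20:10 | 12.22 | 3.67 | 8.55 |

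All three rows are 30:30 over the whole trial, so overall counterbalancing alone does not fix the contrast. The uneven splits are illustrations, not predictions.

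**4. Order effect in the drug difference.** Let θ be the drug effect and δ the session 1 minus session 2 difference that would appear without drug. In same-cycle women δ includes both order and cycle day. The THC-minus-placebo difference is θ + δ if THC comes first and θ − δ if placebo comes first, so the group mean is θ + (2p − 1)δ. At p = 1/2 the δ term vanishes. At p = 2/3 in LFG and 1/3 in EFG, with the same δ in both, the phase contrast is off by δ/3 + δ/3 = 2δ/3. The documents give no value for δ.

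**5. What the model sees.** With only an EFG/LFG label, a THC dose on day 9 and one on day 14 have the same estradiol value. The estradiol drawn at each session would separate them, but the model as coded does not use it.

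**The case against.** - **The whole window is described as high-estradiol.** The protocol treats all of days 9–14 as peaking or just past the peak, and Aim 1 contrasts high with low estradiol without asking for a dose on the peak day. This stands. A reader might infer that about half of LFG THC doses miss the peak, but that needs a peak day which the documents do not give. With LFG pairs weighted equally, the share off-peak would be 0% for a peak spanning days 9–14, 33% for days 10–14, 50% for days 13–14, 83% for days 12–13 and 100% for days 11–12.
- **No dilution against the planned window.** This also stands. With 1:1 order the feasible pairs average day 11.5, which is the window midpoint, (9 + 14)/2. One could assume that the estradiol rise on days 9–10 is a fraction f of that on days 13–14 and compute a contrast of (1 + f)/2, or 60–80% for f = 0.2–0.6. That measures the plan against a days 13–14 target it never set, with values of f found nowhere in the documents.
- **Same-cycle testing is not required.** Correct. The 4-day minimum also allows testing in different cycles, so the point is conditional and the one-half share cannot be applied to all LFG women.
- **Estradiol is measured, and order is counterbalanced.** Measured estradiol protects the planned correlation with circulating levels, and spread in cycle day may even help it. It does not protect a model that uses the group label. Counterbalancing removes order and cycle-day main effects from the average drug difference. It protects the phase contrast only if it holds within each group. Silence on this is a gap in the text, not evidence of imbalance.

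**Conclusion.** The point holds in conditional form. For any LFG woman tested within one cycle, session order is fully tied to cycle day, her THC and placebo sessions lie 4–5 cycle days apart, and about half of such women take THC at the early end of the window. This rests only on the protocol's own window, gap and counterbalancing, and it survives a one-day shift in how the window is read. As written, the model treats early- and late-window THC doses as one exposure and has no term for order or cycle day. That does not match the Approach, which relates the Aim 1 response to measured baseline estradiol.

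The size of the effect on the Aim 1 result is not established. It depends on the share tested within one cycle, on estradiol by day and on the order split within each group, none of which the documents give. They do not support a statement that a given share of doses misses the estradiol peak, or any percentage loss of contrast. The point is about the model and the wording, and is worth acting on because the remedy is nearly free.

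**What to change.** 1. State that drug order is counterbalanced separately within EFG and within LFG.
2. In the model under Statistical Analyses, use the estradiol measured before the capsule at each session, with the THC-session value as moderator of the drug effect. Add session order or cycle day as a covariate. Keep the EFG/LFG contrast alongside.
3. State whether a woman's two sessions may span cycles, and record the cycle day of each session. If same-cycle testing is used, limit the Aim 1 phase conclusion to the cycle days actually tested.

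Cost: wording, and one or two extra model terms. Because order and THC-session estradiol may be correlated in same-cycle women, the adjusted moderator estimate may be somewhat less precise. No visits, procedures or participants are added.
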